**Exclusion Criteria**

- Under age 13
- History of breast cancer (screen by past medical history)
- History of undiagnosed vaginal bleeding (screen by past medical history)
- Head trauma that affected pituitary function (screen by past medical history)
- Prolactin insufficiency (screen by past medical history)
- Previous lactation failure (defined as no lactation within 5 days postpartum)
- Any contraindication to lactation/implant use including diseases transmittable by breast milk (screen by past medical history)
- Liver dysfunction (screen by past medical history)
- Use of drugs that inhibit lactation (screen by medical history)
- Sensitivity to the components of the ENG implant (screen by past medical history)
- Contraindications to use the implant by the (US MEC) (screen by past medical history)
- Active labor
- Delivery at  $<$  37 weeks gestational age

There is a description of different inclusion/exclusion criteria between the sites. UNM Is recruiting minors under age 18 and over the age of 13, and the University of Utah is not recruiting minors. This is the only difference in the protocols.

4.3. This study will include pregnant adolescent and adult women. This study will not recruit adults who are unable to consent or women who are incarcerated.

4.4. This study will recruit women who can speak and read English and/or Spanish fluently.

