**5. Number of Subjects**

5.1 NA

PROTOCOL TITLE: Effect of immediate versus standard postpartum insertion of the contraceptive implant on breastfeeding outcomes

5.2. This is a multi-site study. Through the University of New Mexico Hospital, its affiliated clinics and the University of Utah and its affiliated clinics. We will recruit up to 200 participants between both study sites.

5.3. Up to 200 participants will be enrolled, with a goal of 75 in each group, to ensure adequate power to determine the primary outcome, after anticipated loss to follow up.

This study is a non-inferiority trial designed to demonstrate that immediate postpartum insertion of the ENG implant is non-inferior to standard ENG implant insertion with respect to the proportion of women who discontinue breastfeeding by 8 weeks after delivery. Discontinuation of breastfeeding under the current treatment, standard insertion, is expected to be 30% based on previous studies (10, 15). To achieve 80% power with a 1-sided Type 1 error of 5% utilizing the Z test (unpooled), 62 participants are required in each group for a total of 124. Accounting for expected loss to follow up of 20%, the total number of participants required is 149, rounded to 150. We intend to enroll up to 200 participants due to unanticipated loss to follow up, so this should ensure that we have enough data for data analysis.

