The questionnaires will contain data about breastfeeding, postpartum depression, and sexual function. A paper diary will be provided to aid the participant in daily recording of data. We will also include a retrospective data collection instrument to account for those we miss at the primary data collection points for breastfeeding information. If the primary questions have been answered either prospectively or retrospectively, then they get the normal prospective survey. If participants do not meet this criteria or if they miss a previous survey, then they will receive a retrospective survey. The diary will be collected at 2, 4, and 8 weeks. If possible, 2-3 good phone numbers will be obtained as well as addresses for each participant. Participants will have a phone number to contact study personnel at their specified site during standard work hours: Monday-Friday 8am- 4:30 pm with any concerns or adverse events. If they call after-hours, a voicemail system will be available, and the participant will be contacted the next working day.

*Data collection instruments*

Data collection instrument	Manner of collection	Timing	Included data
Enrollment form	Medical chart review  In-person, telephone and/or online via UNM's REDCap	After delivery  At enrollment	Participant & neonate medical history, delivery details  contraceptive history, contraceptive bridge-methods, lactation history, lactation and work expectations
Contraceptive Counseling Survey	In-person, telephone and/or online via UNM's REDCap	At enrollment and 4 weeks postpartum	Satisfaction with contraceptive counseling
Breastfeeding Survey	In-person, telephone and/or online via UNM's REDCap	2, 4, 8, 12, 24 weeks postpartum	Breastfeeding continuation, exclusivity, reasons for discontinuation if applicable, infant weight, resumption of intercourse, and satisfaction with contraception
EPDS	In-person, telephone and/or online via UNM's REDCap	2, 4, 8 weeks postpartum	Postpartum depression scale
FSFI	In-person, telephone and/or online via UNM's REDCap	4, 8, 12 weeks postpartum	Sexual function scale

PROTOCOL TITLE: Effect of immediate versus standard postpartum insertion of the contraceptive implant on breastfeeding outcomes

Bleeding diary	Paper or UNM's REDCap	Reviewed at 2, 4, 8 weeks. Collected at 2, 4, and 8 weeks	Bleeding patterns Side effects

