## 13.Data Analysis

13.1 We will conduct a primary analysis per protocol and a secondary analysis per intention to treat. The rationale behind this strategy is to analyze both approaches and examine the result for consistency. A Repeated measures ANOVA analysis will be used for continuation of breastfeeding. To evaluate secondary outcomes between the two

**PROTOCOL TITLE:** Effect of immediate versus standard postpartum insertion of the contraceptive implant on breastfeeding outcomes

groups we will use the T-test, Wilcoxon Rank Sum test, Chi-squared test, or Fisher's exact test as appropriate. Secondary outcomes to be evaluated are to compare time of exclusivity of breastfeeding, mix breastfeeding, factors associated with discontinuing breasts feeding, time of breastfeeding discontinuation and patient satisfaction with postpartum contraception counseling and with timing of placing the implant between both groups. If there are significant differences between treatment groups, multivariable linear (for continuous outcomes) and logistic (for dichotomous outcomes) regression will be utilized in addition to control for confounding.

13.2 This study is a non-inferiority trial designed to demonstrate that immediate postpartum insertion of the ENG implant is non-inferior to standard ENG implant insertion with respect to the proportion of women who fail to breastfeed by 8 weeks after delivery. The failure rate for continuation of breastfeeding under the current treatment, standard insertion, is expected to be 30%.

The following sample size determination and plan for data analysis was developed in conjunction the University of New Mexico Clinical and Translational Science Center (CTSC). The non-inferiority margin for both primary outcomes is 15%, meaning that immediate insertion can be regarded as non-inferior (in terms of breastfeeding continuation) to standard insertion if the difference in rate with immediate insertion is no more than 15% worse than with standard insertion. To achieve 80% power with a 1-sided Type 1 error of 5% utilizing the Z test (unpooled) 62 participants are required in each group for a total 124. Accounting for the expected loss of follow up of 20%, the total subjects 149, round to 150. We intend to enroll up to 200 participants due to unanticipated loss to follow up, so this should ensure that we have enough data for data analysis.

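### Section 13.1 makes covariate adjustment depend on a significance test of the data; a short fixed covariate list should be adjusted for in every main comparison

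*Combined protocol and SAP*

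**What the plan says.** Section 13.1 assigns one method to breastfeeding continuation: "A Repeated measures ANOVA analysis will be used for continuation of breastfeeding". For the secondary outcomes the tests are unadjusted: "groups we will use the T-test, Wilcoxon Rank Sum test, Chi-squared test, or Fisher's exact test as appropriate". After listing those outcomes it adds: "If there are significant differences between treatment groups, multivariable linear (for continuous outcomes) and logistic (for dichotomous outcomes) regression will be utilized in addition". The sentence closes by giving the purpose as control of confounding, so regression supplements the unadjusted tests and does not replace them.

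No covariate is named and no significance level is set for the condition. The section does not say whether the differences that trigger regression are in baseline characteristics or in outcomes, or which result counts if the adjusted and unadjusted analyses disagree. Nowhere do the documents prespecify adjustment for site or any baseline variable, and no stratification of randomisation by site is stated.

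Usable baseline data are already collected. The instruments table in Section 12 has the enrolment form record "contraceptive history, contraceptive bridge-methods, lactation history, lactation and work expectations". There are two sites, and the note after the exclusion criteria in Section 4.2 says they differ in case mix: "UNM Is recruiting minors under age 18 and over the age of 13, and the University of Utah is not recruiting minors".

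**The concern.** A significance test is a poor way to decide on adjustment, whichever differences are meant.

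- **Baseline differences.** Under valid randomisation these arise by chance. Testing for them selects covariates by the size of a chance imbalance, not by how well they predict breastfeeding. A strong predictor that happens to be balanced is left out, and its precision gain is lost.
- **Outcome differences.** Adjustment would then be done only where a difference is already significant. Sections 1.2 and 1.3 hypothesise non-inferiority for the primary outcome and no significant difference for bleeding, sexual function and mood. The results the trial hopes for would go unadjusted.

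The placement of the sentence adds a gap. It may govern only the secondary outcomes, and then the primary comparison has no planned adjustment of any kind.

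At stake are some precision in a trial whose conclusion rests on a confidence limit against a 15-point margin, and the freedom to choose covariates and the deciding result after seeing the data.

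**Working it through.** **Inputs from the documents.** Discontinuation of 30% under standard insertion (Sections 5.3 and 13.2); a 15-point margin, one-sided 5% error, 80% power, an unpooled Z test and 62 per group (Section 13.2); 20% loss and up to 200 enrolled (Sections 5.3 and 13.2).

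**Assumption.** The share of outcome variance explained by baseline covariates, R², is not given. I use 0.05, 0.10 and 0.20.

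**1. The plan's own figure.** With equal true rates, n per group = 2 × 0.30 × 0.70 × (1.645 + 0.842)² / 0.15² = 115.4, so 116, not 62. The figure of 62 comes out if continuation is assumed to be 75% with immediate and 70% with standard insertion: (0.1875 + 0.21) × (1.645 + 0.842)² / 0.20² = 61.4, so 62. The documents do not state that assumption. This is a separate problem, but it sets the starting point below.

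**2. Precision given up by not adjusting.** Power = Φ(0.15 / √(0.42 × (1 − R²) / n) − 1.645), with equal rates. Eighty per arm is 200 enrolled less 20%, halved.

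| R² | Power, 62 per arm | Power, 80 per arm | n per arm for 80% power |
|---|---|---|---|
| 0 | 57.0% | 66.5% | 116 |
| 0.05 | 58.9% | 68.4% | 111 |
| 0.10 | 60.9% | 70.4% | 105 |
| 0.20 | 65.3% | 74.8% | 93 |

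The last column is 116 × (1 − R²), rounded up. Under the unstated 75% against 70% assumption, power at 62 per arm is 80.3%, 82.1%, 83.8% and 87.4% for the same R² values.

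**3. How often a baseline trigger fires by chance.** For k independent tests at 5%, the chance is 1 − 0.95^k: 5% for k = 1, 22.6% for k = 5 and 40.1% for k = 10. Both k and the 5% level are assumptions.

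**4. What the triggers do.** I simulated 8,000 trials per scenario at 62 per arm, with one standard-normal baseline covariate (log-odds slope 0.5, 0.8 or 1.2), a linear model with robust standard errors, and triggers at two-sided 5%.

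| Rule | Power, equal arms | Type I error, true deficit of 15 points |
|---|---|---|
| Never adjust | 57–58% | 4.8–5.5% |
| Always adjust | 59–65% | 4.7–5.2% |
| Adjust on a baseline trigger | 58–59% | 4.3–5.4% |
| Adjust on an outcome trigger | 57–58% | 4.8–5.5% |
| Success on either result | not a planned rule | 6.3–6.9% |

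The simulation standard error near 5% is √(0.05 × 0.95 / 8,000), about 0.24 points. The outcome trigger fires in about 5% of trials when the arms are equal and in about 41–43% when the true deficit is 15 points.

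The triggered rules keep type I error near nominal but lose nearly all the gain from adjusting. Error rises only if success may be claimed on whichever result is favourable.

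**The case against.** Several objections carry weight.

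- **The regression is supplementary.** The stated purpose, "regression will be utilized in addition to control for confounding", keeps the unadjusted tests and points towards the baseline reading. An unadjusted comparison in a randomised trial is valid. This stands. A reader might infer that non-inferiority would always be concluded without adjustment, but that needs the outcome reading, which the text does not establish.
- **The primary endpoint may be outside the rule.** The sentence follows the secondary outcomes, and continuation has its own method. A reader might infer that the condition governs the 8-week comparison against the margin; the documents do not say so. The remaining alternative is that no adjusted primary analysis is planned.
- **No error inflation is shown.** A reader might infer that the data-driven trigger makes the trial anti-conservative. The simulation does not support that. Inflation needs a rule allowing success on either result, which the plan neither states nor excludes.
- **The low power has another cause.** A reader might blame the adjustment rule for the 57.0%. It comes from the sample-size calculation, and adjustment with R² of 0.20 still needs 93 per arm.
- **The gain may be small.** The power figures compare always adjusting with never adjusting, under assumed R². Eligibility narrows the prognostic spread: all women intend to breastfeed, and previous lactation failure is excluded. The low end of the range may be the realistic one.

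These points limit the size of the concern. They do not supply the missing covariate list or say which result decides. The per-protocol primary analysis also weakens the appeal to randomisation, because exclusions after randomisation can create real imbalance; fixed adjustment is only a partial remedy for that.

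**Conclusion.** The concern holds in a limited form. Section 13.1 makes adjustment conditional on a significance test, so whether it is done depends on the data on either reading. The covariates and the deciding result are not fixed in advance, and the primary endpoint may have no planned adjustment.

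The cost is modest. At 62 evaluable per arm with equal 30% discontinuation, adjusting every time adds 1.9 to 8.3 points of power (57.0% to between 58.9% and 65.3%). At 80 per arm it also adds 1.9 to 8.3 points (66.5% to between 68.4% and 74.8%). Both ranges rest on an assumed R² of 0.05 to 0.20. Adjustment does not cure the sample-size shortfall, and the trigger alone is not evidence of an inflated type I error.

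**What to change.** 1. Delete the condition in Section 13.1.
2. Prespecify a short fixed covariate list from data already held: site and lactation history, with age if numbers allow. Define the coding, including how women with no earlier birth are classed. At 30% discontinuation, 124 evaluable women give about 37 discontinuations (0.30 × 124), so the list must stay short.
3. Apply the list in every analysis of the 8-week comparison and of the main secondary comparisons.
4. For the primary, report a risk difference standardised from the logistic model, with its confidence limit against the 15-point margin. An odds ratio alone cannot be read against that margin.
5. Name the adjusted result as the one that decides, before any outcome data are compared by arm, and show the unadjusted result as a sensitivity analysis.

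The cost is revised wording and a little more programming; no new data are needed. The downside is that a model-based estimate replaces the simple comparison as the main result. The primary method also has to be restated, because Section 13.1 now names repeated measures ANOVA while Section 13.2 sizes the trial on a Z test.

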## **14. Provisions to Monitor the Data to Ensure the Safety of Subjects**

A Data and Safety Monitoring Plan has been developed and will be led by [name] at the University of New Mexico, who is an independent physician. [name] will monitor the study at least quarterly.

The ENG implant is an FDA approved drug, which has a well-established record in breast feeding women. Early implant insertion reflects standard practice in many centers, including the University of New Mexico. The data monitored and reviewed will include enrollment and dropout rates, protocol deviations, review of subject symptoms, and preliminary analysis of the primary outcomes (continuation of breastfeeding at 8 weeks). The reports will include enrollment and dropout rates, protocol deviations, review of subject symptoms, and preliminary analysis of the primary outcomes. The trial will be stopped for a cessation of breastfeeding in more than 70% of the early insertion group in the first 8 weeks. Any additional reports to the IRB will occur in response to specific events adverse events. Any serious adverse event defined as an event requiring re-hospitalization will require re-evaluation of the risk determination and continuation of the study. Adverse event reporting will follow

**PROTOCOL TITLE:** Effect of immediate versus standard postpartum insertion of the contraceptive implant on breastfeeding outcomes

guidelines as proposed by Good Clinical Practice and collected as they occur or are reported by patients. These reports will be compiled for review by the DSMB quarterly; except for serious adverse events which will be reported to the IRB and DSMB within 24 hours of the occurrence. All subjects will have access to clinical care which is not dependent on study participation and will be notified of the availability of that care. All data will be collected for quarterly reporting to the DSMB as well as for final data analysis and reporting. There may be times when we are required by law to share information. However, protected health information (PHI) will not be used in any published reports about this study.

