## 7. Study Endpoints

	Screen -ing	First 24 hours Post partu m	1-7 days*	2 weeks	4 weeks	6 weeks	8 weeks	12 weeks	24 weeks END	Up to 1 year pp	Up to 5 years pp
Intake	X										
Postpartum contraception counseling satisfaction survey	X				X						
Device Insert		X			X	X					
Exclusive breastfeeding			X	X	X		X	X	X		
Breastfeeding discontinuation				X	X		X	X	X		
Retrospective Breastfeeding Discontinuation Chart Review Form										X	
Contraceptive use			X		X		X	X	X		X
Diary collection				X	X		X				
Mood (EPDS)				X	X		X				
Sexual function (FSFI)					X		X	X			
Bleeding log review				X	X		X				

7.1. The primary endpoint of this research are to compare continuation of lactation at eight week postpartum between women in the immediate with standard group.

The secondary endpoints of this research are to compare number of days of postpartum bleeding, postpartum sexual function as measured by FSFI score, and postpartum mood as measured by EPDS score, time to resumption of sexual activity, exclusive breastfeeding method, factors associated with discontinuing breastfeeding, timing of breastfeeding discontinuation, patient satisfaction with postpartum contraception counseling and the implant and patient satisfaction with bleeding pattern between the immediate and standard insertion groups.

As in other studies of breastfeeding and hormonal contraception, we will continue to follow women out to 6 months. A survival analysis will be performed to determine longer-term effect of hormonal contraception on breastfeeding.

**PROTOCOL TITLE:** Effect of immediate versus standard postpartum insertion of the contraceptive implant on breastfeeding outcomes

- 7.2. The primary study endpoint is also a safety endpoint: breastfeeding continuation through 8 weeks. We have developed a Data Safety and Monitoring Plan related to these endpoints (please see below).
- 7.3. No exploratory endpoints will be conducted in this research.

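### The 70% stopping rule in section 14 has no minimum number of women, no defined denominator and no comparator, so it is noise-driven at early looks and weak even if cessation doubles

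*Combined protocol and SAP*

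**What the plan says.** Section 7.2 gives the primary endpoint a second role: "The primary study endpoint is also a safety endpoint: breastfeeding continuation through 8 weeks". It refers the reader to the monitoring plan in section 14.

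Section 14 has the data reviewed at least quarterly by an independent physician, with reports compiled for a DSMB. The reports include a preliminary analysis of the primary outcome. The only numerical stopping criterion is: "The trial will be stopped for a cessation of breastfeeding in more than 70% of the early insertion group in the first 8 weeks". Nothing is said about how many women must have reached 8 weeks, who is in the denominator, how a missing 8-week answer counts, or what the standard arm is doing at the time. No error rate or trigger probability is given.

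Section 13.2 supplies the figures against which the trigger can be judged. "The failure rate for continuation of breastfeeding under the current treatment, standard insertion, is expected to be 30" percent, and "The non-inferiority margin for both primary outcomes is 15" percentage points, so that immediate insertion is acceptable "if the difference in rate with immediate insertion is no more than 15% worse than with standard insertion". The edge of the acceptable range is therefore 30% + 15 points = 45% cessation. The plan works with 62 evaluable women per group, and section 5.3 enrols "with a goal of 75 in each group".

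**The concern.** The wording is mandatory and rests on a raw proportion in one arm. Three things follow.

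- Without a minimum number, a first quarterly review with a handful of 8-week outcomes can cross 70% by chance when nothing is wrong.
- With larger numbers, the observed proportion settles near its true value. The rule then rarely fires unless true cessation is itself close to 70%, so a large harm below that level usually passes.
- Without a comparator, the rule answers a different question from the trial's. If 72% stopped in both arms, the trial would have to stop with a between-arm difference of zero. If 60% stopped with immediate and 30% with standard insertion, the difference would be twice the margin and the rule would be silent.

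At stake are a needless early stop and weak written protection on the endpoint that the plan itself names as its safety endpoint.

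**Working it through.** **Inputs.** Trigger: more than 70% of the early group (section 14). Expected cessation 30% and margin 15 points (section 13.2). Evaluable women per group 62 (section 13.2); enrolment goal 75 per group (section 5.3). Review at least quarterly (section 14); recruitment within one year (section 6.1). The plan states no operating characteristic for the rule, so there is no figure of its own to reproduce. The 62 is taken as given; whether it follows from its stated inputs is a separate matter and does not affect these results.

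**Formula.** With n evaluable women and true cessation p, the rule fires at a single look with probability P(X ≥ r), where X is binomial(n, p) and r is the smallest whole number with r/n > 0.70.

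**Step 1: chance stops at the expected 30%.**
- n = 1, r = 1: 0.30 = 30%.
- n = 2, r = 2: 0.30² = 9.0%.
- n = 3, r = 3 (2 of 3 is only 66.7%): 0.30³ = 2.7%.
- n = 4, r = 3: 4 × 0.30³ × 0.70 + 0.30⁴ = 0.0756 + 0.0081 = 8.4%.
- n = 5, r = 4: 5 × 0.30⁴ × 0.70 + 0.30⁵ = 0.02835 + 0.00243 = 3.1%.
- n = 10, r = 8: 0.16%.
- n = 20, r = 15: 0.004%.

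Each figure is for one look at that n. They are not cumulative.

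**Step 2: is a very small first look plausible?** Assume steady entry of 75 early-arm women over 52 weeks and a first review at 13 weeks. Only women who delivered in the first 13 − 8 = 5 weeks can have an 8-week outcome: 75 × 5/52 ≈ 7 women, or about 6 after 20% loss. Section 20.1 expects most women to be enrolled antenatally, so the number would be lower if the review clock starts at first enrolment.

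**Step 3: firing under real harm, single look.**

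| n | r | true 45% | true 60% |
|---|---|---|---|
| 20 | 15 | 0.64% | 12.6% |
| 62 | 44 | 0.003% | 4.9% |
| 75 | 53 | 0.0006% | 3.7% |

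A true 60% is twice the expected rate and 60 − 30 = 30 points worse, against a margin of 15.

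**Step 4: repeated looks.** The plan does not fix the number or timing of looks, so two schedules are assumed. The entries are the chance of ever crossing.

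| Looks at n = | true 30% | true 45% | true 60% |
|---|---|---|---|
| 19, 38, 56, 75 | 0.01% | about 1% | 22% |
| 12, 25, 38, 50, 62, 75 | about 0.2% | about 4% | 31% |

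Adding a first look at n = 5 to the four-look schedule raises the chance of a stop at a true 30% from 0.01% to 3.1%. Nearly all of that is the 3.1% from the first look itself.

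**Step 5: the denominator matters.** Take 75 randomized to immediate insertion, 62 with an 8-week answer and 13 without.
- If 44 of the 62 have stopped, 44/62 = 71.0% fires but 44/75 = 58.7% does not.
- If 40 of the 62 have stopped, 40/62 = 64.5% does not fire. Counting the 13 missing as stopped gives 53/75 = 70.7%, which does.

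The same data can stop or continue the trial depending on a convention that is not written down.

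**The case against.** **A harm rule need not fire at the margin.** This stands. A reader might infer that the 70% trigger contradicts the 45% that follows from section 13.2, or that the plan regards 45% as inferior and fails to act on it. The documents support neither. Section 13.2 treats a difference of up to 15 points as acceptable, so 45% lies at the edge of the tolerated range. An interim stop for extreme harm and a final non-inferiority margin do different jobs, and silence at 45% is not a defect.

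**A single late look understates the rule.** This also stands. A reader might infer from the 4.9% at 62 women that a doubling of cessation would nearly always pass. Looks accumulate, and over the assumed schedules the chance of firing at 60% is about 22% to 31%. By 62 women recruitment would be nearly over, so that look matters least. Even so, 22% to 31% means that a doubling passes in roughly seven or eight trials out of ten.

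**The monitor already sees more than this rule.** Partly right. The reports contain a preliminary analysis of the primary outcome, and that endpoint is a between-arm comparison. It would be wrong to infer that the monitor has no comparative information. But no stopping criterion is attached to that analysis, and the one criterion that is written is mandatory.

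**No sensible monitor would stop on four women.** Probably so, and by 10 women the chance stop at 30% is already only 0.16%. The plan should then say so, because its wording leaves no such discretion.

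**A comparative rule is not automatically powerful.** Fair. As an illustration, stopping when the unpooled standardised difference exceeds 3 would fire at 60% versus 30% about 69% of the time with 62 per arm, but only about 21% with 20 per arm. At 45% versus 30% with 62 per arm it fires about 12%. False triggering is about 0.19% per look at 62 per arm and 0.30% at 20. The stronger arguments for a comparator are that it asks the right question and that its behaviour can be stated in advance.

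**Conclusion.** The point holds as a weakness in the monitoring rule. As written, the only stopping criterion can be met by chance on the first few women: 30%, 9.0%, 2.7% and 8.4% at 1 to 4 women when the true rate is the expected 30%. It gives limited protection at a true 60%: 12.6% at 20 women and 4.9% at 62 for a single look, and about 22% to 31% over four to six looks. It cannot tell an implant effect from low continuation in both arms, and its result can turn on an undefined denominator.

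The small-number figures rest on a literal reading of section 14. They largely disappear once 10 to 20 women are evaluable. The repeated-look figures rest on assumed schedules, and all figures assume independent women with a common cessation probability. No effect on the final analysis is shown. The change is worth making because the trigger is mandatory and the remedy is cheap.

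**What to change.** In section 14:

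1. Apply the rule only once a stated minimum number of women per arm have 8-week outcomes.
2. State the denominator (randomized, implant placed, or followed to 8 weeks) and how missing outcomes count.
3. Base the rule on the immediate-minus-standard difference in cessation, using the preliminary primary-outcome analysis that the monitor already receives.
4. State the planned looks and report the chance of triggering over them with 30% in the standard arm and 30%, 45% and 60% in the immediate arm.

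The independent monitor sets the threshold. A boundary of 3 standard errors or a minimum of 20 per arm would be illustrative only.

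The cost is a by-arm table in each quarterly report and a little more work on the monitoring plan. No new visits or data are needed.
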